9.1.2 Serious Adverse Event

A serious adverse event is any adverse event occurring at any dose that results in any of the following outcomes: death, a life-threatening adverse event, inpatient hospitalization or prolongation of existing hospitalization, a persistent or significant disability/incapacity, or a congenital anomaly/birth defect. Important medical events that may not result in death, be

life-threatening, or require hospitalization may be considered a serious adverse event when, based upon appropriate medical judgment, they may jeopardize the patient and may require medical or surgical intervention to prevent one of the outcomes listed in this definition. (See Section 9.3 for procedures for reporting a serious adverse event.)

Allergan considers all cancer adverse events as serious adverse events. In addition, Allergan considers any abortion (spontaneous or nonspontaneous) as a serious adverse event.

Pre-planned surgeries or procedures for pre-existing, known medical conditions for which a patient requires hospitalization is not reportable as a serious adverse event.

Any pre-planned surgery or procedure should be clearly documented in the site source documents by the medically qualified investigator at the time of the patient's entry into the study. If it has not been documented at the time of the patient's entry into the study, then it should be documented as a serious adverse event and reported to Allergan.

9.1.3 Severity

A clinical determination will be made of the intensity of an adverse event. The severity assessment for a clinical adverse event must be completed using the following definitions as guidelines:

Mild	Awareness of sign or symptom, but easily tolerated.
Moderate	Discomfort enough to cause interference with usual activity.
Severe	Incapacitating with inability to work or do usual activity.
Not applicable	In some cases, an adverse event may be an 'all or nothing' finding which cannot be graded.

9.1.4 Relationship to Study Drug or Study Procedure

A determination will be made of the relationship (if any) between an adverse event and the study drug or study procedure, as applicable. A causal relationship is present if a determination is made that there is a reasonable possibility that the adverse event may have been caused by the drug or study procedure.

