9.3 Procedures for Reporting a Serious Adverse Event

Any serious adverse event occurring during the study period (beginning with informed consent) and for at least 12 weeks after the last dose of study drug must be immediately reported but no later than 24 hours after learning of a serious adverse event. Serious adverse events must be reported to Allergan recorded on the Serious Adverse Event Form (GSE-SIMR-F-011). All patients with a serious adverse event must be followed up and the outcomes reported. The investigator must supply Allergan and the IRB with any additional requested information (eg, autopsy reports and discharge summaries).

In the event of a serious adverse event, the investigator must:

1. Notify Allergan immediately by fax or email using the Serious Adverse Event Form (GSE-SIMR-F-011) (contact details can be found on page 1 of the Serious Adverse Event Form); phone numbers and relevant Allergan personnel contacts are also on the front page of protocol.
2. Obtain and maintain in his/her files all pertinent medical records, information, and medical judgments from colleagues who assisted in the treatment and follow-up of the patient.
3. Provide Allergan with a complete, written description of the adverse event(s) on the serious adverse event form describing the event chronologically, including any treatment given (eg, medications administered, procedures performed) for the adverse event(s). Summarize relevant clinical information about the event: signs, symptoms, diagnosis, clinical course and relevant clinical laboratory tests, etc. Include any additional or alternative explanation(s) for the causality which includes a statement as to whether the event was or was not related to the use of the investigational drug.
4. Promptly inform the governing IRB of the serious adverse event as required by the IRB, local regulations, and the governing health authorities.

10. Administrative Items

This protocol is to be conducted in accordance with the applicable Good Clinical Practice (GCP) regulations and guidelines, eg, the International Conference on Harmonisation (ICH) Guideline on GCP.

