The patient should be supine for injection into the corrugators muscle. This muscle will be injected with 0.1 mL per site, bilaterally for a total of 2 injection sites (Figure 3). The corrugators muscle injection site is located approximately 1 finger's breadth (~1.5 cm) above the medial superior edge of the orbital ridge (bony landmark). Inject with the bevel of the needle pointing upward at a 45-degree angle away from the medial aspect of the muscle to avoid ptosis of the eyelid. Pinching the muscle may help adjust the depth of the needle insertion and reduce pain. Inject the needle halfway to the hub – stay superficial.

[figure not shown]
Figure 3 Corrugator Muscle FSFD Injection Sites

Procerus

The patient should be supine for injection into the procerus muscle. This muscle will be injected with 0.1 mL for a total of 1 injection site located midline to the forehead (Figure 4). The insertion site for the procerus muscle injection is midline on the forehead, approximately 1 finger's breadth (~1.5 cm) above and midline to the medial superior aspect of the orbital ridge (bony landmark) of each eye. The injection site for this muscle should be approximately midway between the 2 corrugator injections (visualize a single straight line connecting all 3 of these injections). Inject with the bevel of the needle pointing directly upward. Inject the needle halfway to the hub – stay superficial.

[figure not shown]
Figure 4 Procerus Muscle FSFD Injection Sites

Frontalis

The patient should be supine for injection into the frontalis muscle. This muscle will be injected both medially and laterally with 0.1 mL per site, bilaterally for a total of 4 injection sites (Figure 5). For the medial injection sites, visually draw a line up from the medial edge of the orbital ridge. The injection site is approximately 1 finger's breadth (~1.5 cm) above the corrugators injection site. The lateral injection is parallel and approximately 1 finger's breadth (~1.5 cm) lateral to the first 2 injections. Make sure with these injections that the needle stays superficial to avoid the periosteum. A good rule of thumb is to inject superficially enough to raise a bleb. A common mistake is to inject the frontalis muscle too low, which can result in eyebrow ptosis. Go higher on the muscle than you may be first inclined to inject. The bevel of the needle should point upward for these injections.

Figure 5 Frontalis Muscle FSFD Injection Sites

[figure not shown]

Temporalis

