### **9.1.1. Incidence of Adverse Events**

All AEs will be summarized for the Safety Set in the manner described in Section 9. Counts and percentage of patients with each type of AE will be provided. Denominators for percentages will be the total number of patients treated in each arm or overall. At each level of patient summarization, a patient is counted once if the patient reported one or more events.

An overview summary of the number and percentage of patients with any TEAE, serious TEAE, study drug-related TEAE, study drug-related serious TEAE, TEAE leading to treatment discontinuation, TEAE leading to study discontinuation, and AE leading to death will be provided by treatment arm.

Treatment-emergent AEs will also be summarized separately for each injection cycle for BOTOX treated patients.

The following summary tables will be repeated for any TEAE, serious TEAE, study drug-related TEAE, study drug-related serious TEAE, TEAE leading to treatment discontinuation, TEAE leading to study termination, and AE leading to death.

Summaries of the total number of TEAEs and the number and percentage of patients with at least one TEAE will be provided by treatment group. The number and percentage of patients and the number of events will also be presented by SOC and PT in descending order from the SOC with the highest total incidence (that is, summed across all treatment groups) to the SOC with the lowest total incidence. If the total incidence for any 2 or more SOCs is equal, the SOCs will be presented in alphabetical order. Within each SOC, the PTs will be presented in alphabetical order. At each level of patient summarization, a patient is counted once if the patient reported one or more events.

All AEs, will be presented in a by-patient listing.

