### **9.1.2. Relationship of Adverse Events to Study Drug**

A summary of TEAEs by relationship to study drug will be presented in a table by incidence of occurrence. The relationships will be collected as the possibility that study drug caused the event

and will be reported as “Related” or “Not Related”. In the TEAE relationship table, if a patient reports multiple occurrences of the same AE, only the most closely related occurrence will be presented. Treatment-emergent AEs that are missing a relationship will be presented in the summary table as “Related”, but will be presented in the data listing with a missing relationship. Percentages will be calculated by the number of patients in the Safety Set. Denominators for percentages will be the total number of patients treated in each arm or overall.

The TEAE data will be categorized and presented by SOC, PT, and relationship in a manner similar to that described in Section 9.1.1.

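### The SAP tabulates adverse events related to study drug only, while the protocol counts drug or procedure, so BOTOX events blamed solely on the injection would appear as unrelated

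*Protocol*

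**What the plan says.** Protocol 9.1.4 asks for a judgement on the "relationship (if any) between an adverse event and the study drug or study procedure, as applicable". It sets one causality test: the event is related if "there is a reasonable possibility that the adverse event may have been caused by the drug or study procedure". Either source is enough.

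SAP 9.1.2 is headed as relationship to study drug. It states: "The relationships will be collected as the possibility that study drug caused the event". The answer has two levels, "and will be reported as “Related” or “Not Related". Blanks are handled conservatively: "Treatment-emergent AEs that are missing a relationship will be presented in the summary table as “Related". SAP 9.1.1 carries the same label into the overview table and the tables by system organ class and preferred term: "study drug-related TEAE, study drug-related serious TEAE".

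The readable SAP text has no procedure category, no procedure table, and no rule mapping procedure-related events to either answer. SAP Section 11 lists one departure from the protocol, the dropping of the ssITT and per-protocol analyses.

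The protocol does not carry its own two-part test through. Section 9.2 speaks of drug-related events for IRB reporting, and Section 9.3 asks in the serious-event report for "a statement as to whether the event was or was not related to the use of the investigational drug".

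**The concern.** Section 7 of the protocol says the SAP will elaborate the protocol's principal features. Here the SAP narrows a definition without saying so.

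The narrowing does not fall equally on the two treatments. A BOTOX session consists of 31 intramuscular injections, and patients randomized to BOTOX have three sessions. Topiramate is swallowed. An investigator who blames an event on the injection and not on the toxin has a place for that view under protocol 9.1.4, but none under SAP 9.1.2 except *Not Related*.

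At stake is the fairness of the related-event comparison. One arm's administration harms can drop out of the related column, and the other arm has no administration procedure to lose events from. The trial is open-label, so attribution is made with the treatment known. That is a further reason to fix the convention in writing.

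**Working it through.** The plan has no figure to reproduce here, so the check is a comparison of texts.

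| Item | Protocol | SAP |
|---|---|---|
| Cause assessed | Drug or procedure (9.1.4) | Drug (9.1.2) |
| Answers | Causal relationship present or not | Related or Not Related (9.1.2) |
| Serious-event statement | Use of the investigational drug (9.3) | Drug-related serious TEAE (9.1.1) |
| Difference declared | – | No (Section 11) |

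**Step 1. Trace one event.** Take needle-site pain that the investigator ascribes to the injection alone. Under protocol 9.1.4, reading the injection as a study procedure, it is causally related. Under SAP 9.1.2 the question is whether the drug may have caused it; the answer is no, and the event is tabulated as *Not Related*. The missing-data rule does not help, because the field has been completed.

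**Step 2. Which way can the error run?** Only BOTOX is given by an administration procedure. The step that loses the event has no counterpart for an oral tablet, so any undercount of administration harms is an undercount for BOTOX.

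**Step 3. Which tables are touched?**
- Related TEAEs and related serious TEAEs (SAP 9.1.1, 9.1.2): yes.
- All TEAEs, including those by BOTOX injection cycle (SAP 9.1.1): not filtered on relatedness in patients randomized to BOTOX.
- AEs leading to treatment discontinuation (SAP 9.1.5): selected on the action taken with study drug, not on cause.
- Efficacy: not touched.

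**Step 4. Can it be sized?** Let k be the number of BOTOX-treated patients whose only related TEAE is ascribed to the injection alone, and N the BOTOX denominator. The related-TEAE rate is then too low by 100 × k / N percentage points. With N = 200, the planned arm, one patient is worth 100 × 1/200 = 0.5 point. If 2%, 5% or 10% of patients were affected (pure assumptions), k would be 200 × 0.02 = 4, 200 × 0.05 = 10 or 200 × 0.10 = 20, and the shortfall 2, 5 or 10 points. The output simply returns the assumption. N is also not 200 in these tables: SAP Section 9 counts everyone who received BOTOX, including patients who switched from topiramate.

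**The case against.** The strongest reply is that injecting BOTOX *is* giving the study drug. No readable text defines study procedure. The protocol's visit schedule calls day 1 the first administration of study drug, and the phrase in protocol 9.3 refers to use of the drug, which can naturally include how it is given. An investigator who thinks this way would mark injection pain as *Related*. The eCRF is not in the documents, and the text of the protocol's safety sections (6.2 and 7.3.3) is not available. If the form has a single field worded as in 9.1.4, the SAP label is only loose shorthand.

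This stands as a limit on certainty. It does not settle the matter, because 9.1.4 names drug and procedure separately and the SAP says what is collected. Leaving the convention to each site is itself the defect.

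Three stronger readings are tempting and are not supported:
- *That the tolerability hypothesis is biased.* Protocol 2.2 rests it on rates of adverse events and of discontinuations due to them, not on related events. SAP Section 9 rules out hypothesis tests on safety.
- *That recognised BOTOX effects such as ptosis would be lost.* Attachment 12.1 says "A common mistake is to inject the frontalis muscle too low, which can result in eyebrow ptosis". That links technique to harm, but ptosis is readily read as the product acting at the wrong site, so it meets the drug-only test. The events at risk are those blamed on the needle alone.
- *That the all-TEAE rate for BOTOX falls through the switchers.* SAP Section 9 assigns their TEAEs from the first BOTOX injection onward by relatedness and gives no rule for an event related to neither drug. But the physician's choices in SAP 9.1 are BOTOX, topiramate or unknown, and events of unknown relationship count in both arms. The text does not show that such events would be lost.

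**Conclusion.** The point holds in a limited form. Protocol and SAP define relatedness differently, the difference is undeclared, and on the SAP's wording it can only lower the BOTOX figures. It affects two sets of descriptive tables, related TEAEs and related serious TEAEs, and no test or efficacy result.

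The conclusion rests on two assumptions: that the BOTOX injection is a study procedure in the sense of protocol 9.1.4, and that sites record causality as SAP 9.1.2 describes. Neither can be checked from the documents. The size is unknown, and a reader should not take any illustrative rate as evidence of a particular spurious advantage for BOTOX. It should be corrected because the change is small and the error is one-sided.

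**What to change.** 1. In SAP 9.1.1 and 9.1.2, define related as related to study drug or to its administration procedure (the BOTOX injection), in line with protocol 9.1.4. Title the tables treatment-related TEAEs and treatment-related serious TEAEs.
2. Show drug-related and procedure-related events as separate sub-rows only if the eCRF records the two separately. Protocol 9.1.4 describes one combined judgement and does not say that it is split.
3. Reconcile the causality statement in protocol 9.3 with 9.1.4.

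The cost is SAP wording, table shells and a phrase in the serious-event report. If only drug relatedness was captured, sites would have to be queried about events marked unrelated after an injection. The BOTOX related-event rate may come out slightly less favourable.

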9.2 Procedures for Reporting Adverse Events

Any adverse event must be recorded on the appropriate eCRF.

All adverse events that are drug-related and unexpected (not listed as treatment-related in the current Investigator's Brochure) must be reported to the governing Institutional Review Board (IRB) as required by the IRB, local regulations, and the governing health authorities. Any adverse event that is marked 'ongoing' at the exit visit must be followed-up as appropriate.

9.3 Procedures for Reporting a Serious Adverse Event

Any serious adverse event occurring during the study period (beginning with informed consent) and for at least 12 weeks after the last dose of study drug must be immediately reported but no later than 24 hours after learning of a serious adverse event. Serious adverse events must be reported to Allergan recorded on the Serious Adverse Event Form (GSE-SIMR-F-011). All patients with a serious adverse event must be followed up and the outcomes reported. The investigator must supply Allergan and the IRB with any additional requested information (eg, autopsy reports and discharge summaries).

In the event of a serious adverse event, the investigator must:

1. Notify Allergan immediately by fax or email using the Serious Adverse Event Form (GSE-SIMR-F-011) (contact details can be found on page 1 of the Serious Adverse Event Form); phone numbers and relevant Allergan personnel contacts are also on the front page of protocol.
2. Obtain and maintain in his/her files all pertinent medical records, information, and medical judgments from colleagues who assisted in the treatment and follow-up of the patient.
3. Provide Allergan with a complete, written description of the adverse event(s) on the serious adverse event form describing the event chronologically, including any treatment given (eg, medications administered, procedures performed) for the adverse event(s). Summarize relevant clinical information about the event: signs, symptoms, diagnosis, clinical course and relevant clinical laboratory tests, etc. Include any additional or alternative explanation(s) for the causality which includes a statement as to whether the event was or was not related to the use of the investigational drug.
4. Promptly inform the governing IRB of the serious adverse event as required by the IRB, local regulations, and the governing health authorities.

10. Administrative Items

This protocol is to be conducted in accordance with the applicable Good Clinical Practice (GCP) regulations and guidelines, eg, the International Conference on Harmonisation (ICH) Guideline on GCP.

10.1 Protection of Human Patients

10.1.1 Compliance with Informed Consent Regulations (US 21 CFR Part 50) and Relevant Country Regulations

Written informed consent is to be obtained from each patient prior to any study-related activities or procedures in the study, and/or from the patient's legally authorized representative. If the patient is under the legal age of consent, the consent form must be signed by the legally authorized representative in accordance with the relevant country and local regulatory requirements.

10.1.2 Compliance With IRB Regulations

This study is to be conducted in accordance with IRB regulations (US 21 CFR Part 56.103). The investigator must obtain approval from a properly constituted IRB prior to initiating the study and re-approval or review at least annually. Allergan or Allergan designee is to be notified immediately if the responsible IRB has been disqualified or if proceedings leading to disqualification have begun. Copies of all IRB correspondence with the investigator should be provided to Allergan or Allergan designee.

10.1.3 Compliance With Good Clinical Practice

This protocol is to be conducted in accordance with the applicable GCP regulations and guidelines.

10.1.4 Compliance With Electronic Records; Electronic Signatures Regulations (US 21CFR Part 11)

This study is to be conducted in compliance with the regulations on electronic records and electronic signature.

10.2 Changes to the Protocol

The investigator must not implement any deviation from or changes of the protocol without approval by Allergan and prior review and documented approval/favorable opinion from the IRB of a protocol amendment, except where necessary to eliminate immediate hazards to

study patients, or when the changes involve only logistical or administrative aspects of the study (eg, change in monitors, change of telephone numbers).

10.3 Patient Confidentiality

A report of the results of this study may be published, but the patient's name will not be disclosed in these documents. The patient's name may be disclosed to the Sponsor of the study, Allergan or Allergan designee, or the governing health authorities or the FDA if they inspect the study records. Appropriate precautions will be taken to maintain confidentiality of medical records and personal information.

10.3.1 Patient Privacy

Written authorization and other documentation in accordance with the relevant country and local privacy requirements (where applicable) is to be obtained from each patient prior to enrollment into the study, and/or from the patient's legally authorized representative in accordance with the applicable privacy requirements (eg, the Health Insurance Portability and Accountability Act Standards for Privacy of Individually Identifiable Health Information ["HIPAA"]).

In accordance with HIPAA requirements, additional purposes of this study may include publishing of anonymous patient data from the study.

10.4 Documentation

10.4.1 Source Documents

Source documents may include a patient's medical records, hospital charts, clinic charts, the investigator's patient study files, as well as the results of diagnostic tests such as X-rays, laboratory tests, and electrocardiograms. The investigator's copy of the case report forms serves as part of the investigator's record of a patient's study-related data.

The following information should be entered into the patient's medical record:

- Patient's name
- Patient's contact information
- The date that the patient entered the study and patient number
- The study title and/or the protocol number of the study and the name of Allergan

- A statement that informed consent and/or assent was obtained (including the date).
A statement that written authorization and local patient privacy required documentation for this study has been obtained (including the date).
- Dates of all patient visits
- Medical history
- All current concomitant medication use, including prescription, OTC, herbal, and illicit drug use
- Past and current headache prophylaxis medication use history, including prescription, OTC, and herbal drug use
- Documentation of all procedures conducted during the course of the study
- Occurrence and status of any adverse events
- The date the patient exited the study, and a notation as to whether the patient completed the study or reason for discontinuation, withdrawal, or loss to follow-up
- The results of laboratory tests performed by the site (eg, urine pregnancy tests)
- Key study variables

